5.4 End of study evaluations following completion of chemoradiotherapy treatment

5.4.1 Evaluations during 1-month (week 10-13) follow up

- Symptom-directed physical examination, if clinically indicated (as detailed in 5.1)
- ECOG performance status
- Pregnancy test
- Adverse events and DLTs since the previous assessment
- New or changes to existing medications

5.4.2 Evaluations during 3-month (week 20-22) follow up

- Symptom-directed physical examination, if clinically indicated (as detailed in 5.1)
- ECOG performance status
- Adverse events and DLTs since the previous assessment
- New or changes to existing medications
- CT scan

5.4.3 Evaluations during 6-month (week 33-35) follow up

• Adverse events since the previous assessment

Follow-up evaluations

Following end of study evaluations patients will return to follow-up as per standard of care in the NHS.

Patients may commence Durvalumab treatment after CRT is completed, even if they are still within the trial follow up window. Treatment with Durvalumab should be documented on the patient's eCRF. Response rates and number of patients who have been prescribed Durvalumab will be reported in the final analysis.

6 EARLY PATIENT WITHDRAWAL

Treatment Withdrawal

During the course of the trial, a patient may withdraw early from treatment. This may happen for a number of reasons, including:

- Unacceptable toxicity
- AE/SAEs requiring discontinuation
- Loss to follow-up
- Significant protocol deviation or inability to comply with trial procedures
- Clinical decision
- Patient decision

When the patient stops treatment, the 'End of Treatment' Form needs to be completed, and any other relevant CRFs (example SAE Form) and the Trial Office notified within 24 hours. The reason for withdrawing from treatment early, should be clearly documented in the medical records.

Patients who have stopped treatment early should continue to be invited to all follow-up visits and assessments, unless patient consent for follow-up is withdrawn.

Participants have the option to consent to NHS Digital follow-up. This will entail completion of a separate tracing sheet which will contain the participant's name and NHS number, and will therefore be kept securely by the Trial Office. This will enable future ethically-approved trials to trace participants' outcome data for long term follow up.

Consent Withdrawal

Consent withdrawal means that a patient has expressed a wish to withdraw from the study altogether. Under these circumstances, the site needs to document all relevant discussions in the patient notes and notify the Trial Office, which will allow the office to mark all future CRFs as not applicable.

Data and samples collected prior to participant consent withdrawal will be used for trial analysis. Participants who initially consented to be registered with NHS Digital or equivalent will remain on the system so that important long term follow up data can be requested from NHS Digital, unless the patient specifically requests that permission is withdrawn to do so.

Under these conditions, Investigators are still responsible for following up any SAEs until resolution.

6.1 Patient evaluability and replacement

Patients will not be replaced since the TiTE-CRM uses all accumulated data. However, the TMG may decide to recruit an additional patient if drop-out occurs early in the treatment schedule for reasons other than a DLT. The dose allocated to the additional patient may not necessarily be the same, as this will be determined by the TiTE-CRM model, taking into account accumulated toxicity data at that time point. In the specific situation where one of the first two patients needs to be replaced, the dose allocated to the additional patient will be 450 mg bd, to ensure this dose level is evaluated before escalating to higher doses as per detailed process in section 17.3.

All patients who receive at least one dose of atovaquone will be evaluable for the safety analysis. All patients who commence chemoradiotherapy treatment within the study will be evaluable for response.

7 SAMPLES FOR LABORATORY ANALYSIS

7.1 Samples to be analysed in local Trust's laboratories

Diagnostic Laboratories

Samples for haematology and biochemistry analysis will be labelled with standard patient identifiers and sent to the local hospital diagnostic laboratory. Results will be processed in the standard way and entered into the routine hospital reporting system. Samples will be stored, held, reported and subsequently destroyed in accordance with standard local laboratory practice.

Pathology

The routine diagnostic pathology samples and additional research samples taken at diagnosis will also be labelled, processed and reported according to local hospital protocols. Where sufficient diagnostic material is available, tissue should also be submitted for central laboratory analysis, as detailed in the following sections and separate Sample Handling Manual.

7.2 Samples to be sent to and analysed in a Central Laboratory

During weeks -2/-3 and week -1, additional blood samples of approximately 25 mL will be taken in order to evaluate plasma atovaquone concentration and hypoxia biomarker levels.

7.2.1 Pharmacokinetic assays

For atovaquone PK studies, plasma will be retained and dispatched to a central laboratory for HPLC plasma atovaquone concentration measurement (refer to Sample Handling Manual for specific details).

7.2.2 Plasma hypoxia marker (miR-210)

For plasma hypoxia biomarker analysis, plasma will be retained and dispatched to a central laboratory for qRT-PCR measurement of miR-210 (refer to Sample Handling Manual for specific details).

7.2.3 Hypoxia metagene expression

In cases with sufficient diagnostic tissue, a section of formalin-fixed paraffin-embedded (FFPE) tissue will be obtained and sent to a central laboratory for tumour tissue extraction and hypoxia metagene analysis using the 3'RNA-seq method. This is the optimal technique available to obtain such data from limited and low quality FFPE tissue samples, as is often the case in NSCLC.

More specifically, a previously validated hypoxia gene expression signature will be measured using diagnostic biopsy FFPE samples. We will utilise 3'RNA-seq as it has clear advantages over alternative and now more dated sequencing and array techniques. 3'RNA-seq can accurately estimate gene expression even if applied to low quality or degraded samples and it requires only 100 pg total RNA input. This is an important consideration in our patient population, as diagnostic tissue can often be very scarce. Importantly, modern RNA-seq techniques are relatively inexpensive and when performed on already obtained diagnostic tissue can be easily incorporated into larger clinical studies, or potentially routine diagnostic work-up thereafter.

We will not require patients to undergo additional tissue sampling in appreciation of the difficulty and often repeated attempts required to obtain sufficient diagnostic tissue in this patient population. Also, given the short time window to get patients on treatment and to start CRT, mandating additional tissue may result in a delay in treatment that we feel would be unacceptable.

7.2.4 Summary of samples/assays to be taken during the study

Time Point	Week -2 or -3	Week -1
Blood sample for PK analysis	х	х
Blood sample for plasma biomarker (miR210)	х	х
Request diagnostic tissue sample for hypoxia metagene	х	

The full list of samples required for central laboratory analysis is as follows:

Trial sites will be provided with a separate Sample Handling Manual with detailed arrangements for sample collection, immediate processing, labelling and shipment. Whenever possible, all blood samples will be taken at the same time as blood samples are taken prior to chemotherapy, therefore minimising discomfort and inconvenience to the patient.

7.3 Labelling and confidentiality of samples sent

All samples sent to central analytical laboratories will be labelled with the trial code, trial patient number, and date taken. Should a laboratory receive any samples carrying unique patient identifiers the recipient must immediately obliterate this information and re-label.

7.4 Clinical reporting of exploratory research assay results

The results of central laboratory research assays are exploratory and are not intended to influence the individual patient's medical care. Findings will not be reported routinely to the responsible clinician except in the unlikely event that the result might be beneficial to the patient's clinical management.

7.5 Trial sample retention at end of study

The Chief Investigator has overall responsibility for custodianship of the trial samples. Laboratories are instructed to retain any surplus samples pending instruction from the Chief Investigator on use, storage or destruction. It is possible that new or alternative assays may be of future scientific interest. At the end of the research study, any surplus samples may be retained for use in other projects that have received ethical approval. Hence, any surplus study samples and study information may be transferred to a licensed tissue bank where they will be stored for use in any future ethically approved medical research. Patients are required to authorise these procedures by signing the consent form. This will identify them by name and/or patient study number, and will be sent to the tissue bank along with their samples. Patients can withdraw permission to use their samples in these ways at any time, without affecting their participation in the study. Banked samples will be managed in accordance with applicable host institution policies and the Human Tissue Act (HTA) requirements.

7.6 Withdrawal of consent for sample collection and/or retention

A patient may withdraw consent to provide samples for research at any time without giving a reason. The Investigator must ensure that their wishes are recorded in the medical record and will inform the Trial Office accordingly. The Investigator should discuss with patients the valuable use of samples that have already been provided and under circumstances where these samples have already been processed, it would not be possible to destroy such samples.

7.7 Correlative hypoxia biomarker studies

Where possible, data from imaging and plasma hypoxia markers from the ARCADIAN trial will be combined with such data obtained from the ATOM trial to increase the patient sample size.

8 INVESTIGATIONAL MEDICINAL PRODUCT (IMP)

The trial is investigating the use of atovaquone suspension in combination with chemoradiotherapy. Atovaquone, cisplatin and vinorelbine are all considered Investigational Medicinal Products (IMPs) in this trial due to the investigation of these drugs being used in a novel combination.

8.1 Treatment dose

Atovaquone

Atovaquone doses to be tested are listed in the table below. The dose received by each participant will be decided per the process detailed in section 17.3. All doses are given orally (PO) and twice daily (BD).

Atovaquone dose level	Atovaquone dose
Level 1 (starting)	450 mg PO BD
Level 2	600 mg PO BD
Level 3	675 mg PO BD
Level 4	750 mg PO BD

Cisplatin and vinorelbine

Two 21-day cycles of cisplatin and vinorelbine chemotherapy will be given concurrently during radiotherapy treatment, as follows:

Chemotherapy agent	Chemotherapy dose	Timing of dose
Cisplatin	80 mg/m ²	Days 1 & 22
Vinorelbine	15 mg/m ²	Days 1, 8, 22 & 29

It is acceptable for chemotherapy to commence up to two days after radiotherapy is started. Any delays to chemotherapy treatment during cycle one should result in a corresponding delay to cycle two (see section 8.3.2).

8.2 Duration of treatment

Atovaquone

Patients will receive two weeks (+/- 7 days) of atovaquone prior to starting CRT, treatment will then continue concurrently with CRT. The last dose of atovaquone will be on the morning of the last fraction of radiotherapy. Total duration of atovaquone treatment will be 59 days (+/- 7 days), unless stopped earlier for toxicity or any other reason.

Cisplatin and vinorelbine

Patients will receive two 21-day cycles of cisplatin/vinorelbine as part of their CRT treatment. Chemotherapy will commence (along with RT) on day 1 in week 1, with the last dose of vinorelbine administered on day 29 (week 5). This will follow two weeks (+/- 7 days) of atovaquone treatment, which will be continued throughout CRT. Altogether, patients will receive chemotherapy on 4 days during the trial (unless omitting doses is clinically indicated). Details of chemotherapy treatment received will be recorded in the eCRF.

8.3 Management of drug administration

Atovaquone

Patients will be instructed to take atovaquone oral suspension twice daily with each dose self-administered using a provided syringe, preferably in the morning and evening, and at approximately the same time each day. The bioavailability of atovaquone is increased up to three-fold when administered with fat containing food. Patients will therefore be asked to take atovaquone with a meal, if possible one containing a high fat content (e.g. butter, whole milk, cheese, ice cream, eggs, etc.).

If a patient misses a dose, the dose should be taken later, provided the patient remembers within four hours. If the patient does not remember within four hours, the missed dose should be omitted. Doses should not be doubled to make up for missed doses. If a patient vomits after taking the suspension, the dose should not be replaced.

Cisplatin and vinorelbine

Cisplatin and vinorelbine chemotherapy should be administered concurrently with radiotherapy, as detailed in section 8.1.2. Cisplatin and vinorelbine will be supplied from hospital stock and administered according to local practice and SmPC guidelines. Dispensing labels must be completed for all patients, but trial-specific labelling of these chemotherapy drugs is not required. On days where chemotherapy is delayed for administrative reasons (for example, holidays or weather), this will not be considered a protocol deviation, provided the full planned dose of radiotherapy is administered. Omissions of cisplatin should be resumed as soon as possible. Single-day vinorelbine omissions due to holidays or weather, or for other clinically indicated reasons do not need to be reinstated.

	Days 1 & 22
Pre-che	emotherapy hydration
•	1 L 0.9% sodium chloride infusion over 2 hours
Pre-che	emotherapy medications
•	Dexamethasone
•	Mannitol (if urine output <100 mL/hr)
•	A 5-HT3 antagonist and NK1 antagonist may be given
Chemo	therapy
•	Cisplatin – 80 mg/m ² infusion in 500 mL of 0.9% sodium chloride over 1 hour
•	Vinorelbine – 15 mg/m ² supervised infusion in 50 mL of 0.9% sodium chloride over 5 minutes
Post-ch	emotherapy hydration
•	Cisplatin – 1 L 0.9% sodium chloride / 10 mmol magnesium sulphate / 20 mmol potassium chloride
	infusion over 2 hours
•	Vinorelbine – 100 mL 0.9% sodium chloride infusion (first 3 minutes supervised at 600 mL/hr, then
	1000 mL/hr to finish)
Take h	ome drugs
•	Dexamethasone
•	Ciprofloxacin
•	Movicol sachet
•	Cyclizine*

	Days 8 & 29
Chemotherapy	
•	Vinorelbine – 15 mg/m ² supervised infusion in 50 mL of 0.9% sodium chloride over 5 minutes
Take ho	ome drugs
•	Ciprofloxacin

See section 10 for details of supportive medications.

* Note that **metaclopramide must NOT be given** as an antiemetic, as it may alter plasma levels of atovaquone (see section 10 for further details).

Patient monitoring and management of hypersensitivity and extravasation will be as per local hospital policy.

8.4 Special precautions

Atovaquone

Unopened bottles of atovaquone have a shelf life of 12 months when stored at room temperature (not exceeding 25°C). If room temperature is expected to exceed this, bottles should be kept in a cool, dark location. Bottles may be refrigerated if necessary, but should never be placed in the freezer. Opened bottles of atovaquone suspension can be stored for up to 21 days at room temperature, but must be kept away from extremes of heat or moisture (so should not be kept, for example, in a bathroom).

Cisplatin and vinorelbine

Refer to cisplatin and vinorelbine SmPCs for special warnings and precautions for use.

8.5 Actual versus ideal body weight

Atovaquone

Not applicable - atovaquone dose will not be adjusted for body weight.

Cisplatin and vinorelbine

Doses of cisplatin and vinorelbine will be calculated for each patient based on actual weight. The patient's weight should be recorded prior to every chemoradiotherapy cycle to determine dose of chemotherapy. See section 8.7 for BSA calculation.

8.6 Dose modification

Atovaquone

If chemotherapy is reduced or stopped, atovaquone should be continued.

If RT is suspended for less than seven consecutive days for reasons other than toxicity, atovaquone treatment can also be suspended (at the clinician's discretion), but restarted with RT.

If RT is interrupted for less than seven days due to toxicity, atovaquone should be stopped when RT is discontinued and not restarted.

Interruptions of RT of greater than seven days for toxicity reasons (related to IMPs, CRT or the combination thereof) are defined as DLTs, in which case atovaquone should be permanently discontinued.

If a patient experiences toxicity that is thought to be directly related to atovaquone treatment and not controlled by supportive medication, then atovaquone should be discontinued, rather than the dose reduced, and it should not be restarted. Investigators are encouraged to discuss such decisions to discontinue atovaquone with the CI. See section 9 for effects defined as dose limiting toxicities and reporting procedure.

Single agent atovaquone treatment is not usually associated with significant side effects and as this drug has been prescribed for many years it has a well-established toxicity profile. It is not expected that addition of atovaquone to CRT will increase side effects, however this may occur and will be reported as part of the safety and DLT assessment, if applicable.

Cisplatin and vinorelbine

The following dose modification schedule is recommended for haematological and biochemical abnormalities on chemotherapy. As each patient's clinical circumstances are unique, these are intended as a guide only.

ANC (x10 ⁹ /L)		Platelets (x10 ⁹ /L)	Chemotherapy dose
≥1.5	And	≥100	100%
<1.5	Or	<100	Delay one week and reassess
<1.0	-	_	Delay one week, give additional 5 days antibiotics and reassess

Haematology for cisplatin:

Haematology for vinorelbine:

ANC (x10 ⁹ /L)		Platelets (x10 ⁹ /L)	Chemotherapy dose
≥1.5	And	≥100	100%
<1.5	And	<100	Omit
Febrile neutropenia	Or	Grade ≥4 haematological toxicity	75%

Renal dysfunction for cisplatin:

Creatinine clearance (mL/min)	Chemotherapy dose
>60	100%
40-60	62.5%
<40	Discontinue

Oto- and neurotoxicity for cisplatin:

Ototoxicity or neurotoxicity	Chemotherapy dose
< Grade 3	100%
≥ Grade 3	Discontinue

Hepatic dysfunction for vinorelbine:

ALT		Total bilirubin	Chemotherapy dose
<5 x ULN	And	<2 x ULN	100%
>5 x ULN	And/or	>2 x ULN	70%

If urea is more than 7.0 mmol/L or creatine clearance drops by 20%, discuss with Principal Investigator. Precede day 8 & 29 vinorelbine with 500 mL 0.9% sodium chloride infusion.

Add daily GCSF if patient has had:

- Previous chemotherapy
- Previous pneumonectomy
- Febrile neutropenia during previous chemotherapy cycle
- Chemotherapy delay of >7 days due to neutropenia
- Grade 4 neutropenia

8.7 Calculating and recalculating BSA/doses

Atovaquone

Not applicable – atovaquone dose is not calculated according to body surface area (BSA).

Cisplatin and vinorelbine

BSA is calculated according to the DuBois and DuBois formula. If a patient's weight changes by \geq 10% from baseline (see section 8.5), then drug doses should be recalculated. If a patient's weight changes by <10% the dose may be adjusted according to local policy/clinician's discretion, but is not an absolute requirement.

8.8 Dose capping and dose banding

Atovaquone

Not applicable – no doses are to be capped/banded.

Cisplatin and vinorelbine

No doses are to be capped.

Dose banding can be applied according to local policy. The Trials Office will request each site to state up front whether or not dose banding will be used.

8.9 Compliance

Atovaquone

Patients will be asked to report if they have any missed doses of atovaquone during their weekly clinic visits. Data should be recorded in the clinical record and entered into an eCRF in order to monitor compliance for dose decisions.

Patients should be asked to bring any unused/remaining trial medicines (empty, open or unopened) with them to each clinic visit. At each visit, the patient's supply of atovaquone should be checked and an additional bottle dispensed if needed prior to the next visit (after first opening, the suspension may only be stored for up to 21 days). The trial visits at which resupply is required will vary between participants, dependent on the duration of atovaquone treatment received prior to starting CRT.

Accountability logs are required for atovaquone. Site staff will collect and measure patient returns which must be recorded on the drug accountability log. Accountability Logs should be returned to the Trial Office as requested.

Cisplatin and vinorelbine

Cisplatin and vinorelbine compliance will be monitored via the clinical record.

8.10 Management of overdose

Atovaquone

There is no specific antidote for atovaquone, however several cases of overdose have been published – none of which resulted in life-threatening or fatal side effects [20]. Patients experiencing toxicities upon mis-dosing or over-dosing will be treated at the discretion of the Investigator with adequate supportive care and followed until full recovery.

Cisplatin and vinorelbine

Refer to guidance provided in the SmPC documents for cisplatin and vinorelbine regarding recommendations following overdose.

Administration of a dose of trial drug exceeding that permitted by the trial protocol should be notified to the Trial Office. Any toxicity resulting from administration of an overdose of trial drug should also be reported as an adverse event/serious adverse event (as appropriate) as per reporting processes detailed in section 14.

9 DOSE LIMITING TOXICITY

9.1 Definition of a Dose Limiting Toxicity

All patients who have received at least one dose of atovaquone will be evaluable for DLTs.

DLTs are defined as any of the following occurring between the start of trial treatment until three months post CRT, and assessed by the Principal Investigator as possibly, probably or definitely related to atovaquone and/or to chemoradiotherapy. If an event is believed to be possibly, probably or definitely related to treatment with Durvalumab rather than trial IMPs, it may be reported as an SAE rather than a DLT.

DLTs will be defined as per NCI CTCAE v4.03 and include:

- Grade \geq 4 absolute neutrophil count (ANC) (<0.5 x 10⁹/L) for >7 days
- Grade ≥3 febrile neutropenia (fever of unknown origin without clinically or microbiologically documented infection) (ANC <1.0 x 10⁹/L, fever ≥38.5°C) lasting >3 days
- Infection (documented clinically or microbiologically) with grade 3 or 4 neutropenia (ANC <1.0 x 10⁹/L)
- Grade \geq 3 thrombocytopenia (platelets <25 x 10⁹/L)
- Clinically significant bleeding attributed to grade 3 thrombocytopenia or requiring platelet transfusion
- Grade ≥3 oesophagitis
- Grade ≥3 pneumonitis onset within 3 months of starting radiotherapy
- Grade ≥3 nausea or vomiting not controlled by optimal outpatient anti-emetic treatment for ≥5 days
- Grade ≥3 diarrhoea despite optimal outpatient anti-diarrhoeal medication use
- Any toxicity causing a delay of radiotherapy completion by greater than one week
- An elevation of ALT or AST >5 x ULN lasting 8 days or more
- A concurrent elevation of ALT or AST (>3 × ULN) and total bilirubin (>2 × ULN) in whom there is no evidence of biliary obstruction or other causes that can reasonably explain the concurrent elevation
- Other grade ≥3 effects thought to be clinically significant and directly related to the combination of atovaquone with chemoradiotherapy

Dose limiting toxicities must be reported within 24 hours of the site becoming aware using the SAE form (even if the event does not meet the definition of an SAE). Scan the form and email as an attachment to [contact].

See section 14 for safety reporting procedures.

DLTs will be processed to support dose decisions according to procedures detailed in Section 17 and the separate Protocol Decision Point Plan.

10 **OTHER TREATMENTS (NON-IMPS)**

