2 TRIAL DESIGN

This is a phase I, single arm, open-label trial that will utilise a TiTE-CRM to determine the maximum tolerated dose (MTD) of atovaquone in combination with concurrent CRT in NSCLC. Twenty evaluable participants will be recruited at two centres.

Twice daily oral atovaquone will be added to standard concurrent CRT: 66 Gy in 33 fractions, once daily, 5 days a week (Monday-Friday), with cisplatin (80 mg/m² IV on days 1 and 22 of CRT) and vinorelbine (15 mg/m² IV on days 1, 8, 22 and 29 of CRT). Whilst awaiting CRT to start, patients will receive two weeks (+/- 7 days) of oral atovaquone to ensure steady state is reached (after seven days). Wherever possible, two weeks of atovaquone treatment should be administered prior to CRT, but in appreciation of the difficulty often experienced in radiotherapy scheduling and planning as well as treatment targets, a +/- 7 days window is permitted. In addition, hypoxia biomarker data will be collected at baseline (start of atovaquone run-in) and following two weeks (+/- 7 days) of atovaquone. Atovaquone will then be continued without break for the duration of CRT with the CRT schedule remaining constant for all patients at both centres. Assessment for DLTs will be from the first scheduled dose of atovaquone until three months after completion of CRT. CT scans performed at the three-month follow up visit will be reviewed to collect tumour response data.

The trial will start at the lowest dose of atovaquone (450 mg BD). Two participants will receive this dose and escalation will only be considered when we have 12 weeks of safety data (a high-risk period of developing dose-limiting toxicity, DLT) for at least one participant at this dose level, thus preventing inappropriate early dose escalation. Following this initial safety run in, eligible patients will be continuously recruited and the TiTE-CRM will be used to recommend the dose of atovaquone for each patient, as detailed in section 17.3.

Refer to the schedule of events and flow chart for details of the study visits and procedures.

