3. STUDY METHODS

3.1 Trial Design/framework

Arcadian is a single arm, open-label phase I dose escalation trial using the Time-To-Event Continual Reassessment Method (TiTE-CRM) i.e. a model-based approach to determine the maximum tolerated dose (MTD) of atovaquone in combination with concurrent CRT in patients with NSCLC.

Patients will receive an oral suspension of atovaquone twice daily. The four atovaquone dose levels to be assessed in the TiTE-CRM is as follows:

Dose level	
1	450 mg
2	600 mg
3	675 mg
4	750 mg

Patients will receive atovaquone alone for 1 to 3 weeks during a run-in period followed by 6.5 weeks of concurrent chemoradiotherapy (CRT). The 6.5 weeks of CRT consists of two cycles: Cisplatin ($80 \text{ mg/m}^2 \text{ IV}$)

on days 1 & 22, Vinorelbine (15 mg/m² IV) on days 1, 8, 22 & 29 and thoracic radiotherapy: 66 Gy in 33 fractions, once daily, 5 days a week (Monday-Friday). Therefore, the total treatment duration is expected to be up to 9.5 weeks.

Patients will have follow-up visits at approximately 1, 3 and 6 months after completion of CRT.

The TiTE-CRM will take into account toxicity from the start of the atovaquone run-in period to 12 weeks (84 days) after completion of CRT, so the end of the toxicity assessment period will be approximately the time of the 3 months post-CRT visit.

The figure below shows the study schema

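### The catch-all DLT item requires a relation to the combination, so it conflicts with the definition's own opening condition and with the atovaquone-only run-in

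*Protocol*

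**What the plan says.** Protocol 9.1 sets two conditions. The event must be on the list: "DLTs are defined as any of the following occurring between the start of trial treatment until three months post CRT". It must also be "assessed by the Principal Investigator as possibly, probably or definitely related to atovaquone and/or to chemoradiotherapy". The list is introduced by "DLTs will be defined as per NCI CTCAE v4.03 and include" and ends with a residual item for anything not named: "Other grade ≥3 effects thought to be clinically significant and directly related to the combination of atovaquone with chemoradiotherapy". The reporting table in Protocol 14.11 and SAP Appendix 4 carry the same residual item.

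The run-in lies inside the window. Protocol 2 says "Assessment for DLTs will be from the first scheduled dose of atovaquone until three months after completion of CRT", and the week -1 visit in Protocol 5.3.2 asks the clinician to identify DLTs. SAP 3.1 describes the same period: "Patients will receive atovaquone alone for 1 to 3 weeks during a run-in period".

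Protocol 8.6 provides for the case "If a patient experiences toxicity that is thought to be directly related to atovaquone treatment and not controlled by supportive medication": atovaquone is then stopped and not restarted. Stopping atovaquone is not itself a listed DLT.

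The model receives a binary DLT indicator (Protocol 17.3). A patient without a DLT counts as a non-event, weighted by the share of the window observed (Protocol 17.2, SAP 6.2).

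**The concern.** The opening condition and the residual item disagree about which cause counts. The first accepts atovaquone alone; the second asks for the combination. In the run-in there is no combination, yet DLTs are to be assessed then. The residual item also asks for a direct relation, where the opening condition accepts a possible one.

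The primary endpoint is the MTD of atovaquone. On the literal text, a listed toxicity caused by CRT alone counts, while an unlisted grade 3 or higher toxicity caused by atovaquone alone does not. Any error from this source goes one way: the DLT rate comes out too low. Two sites could also score the same event differently.

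**Working it through.** The plan gives no figure to reproduce here. The sample size of 20 has no formula, and the priors and simulation results are in SAP Appendix 1, which is a separate document. The check is therefore of wording and scoring, with simple arithmetic.

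**1. Which events fall through.** Take events that the Principal Investigator attributes to atovaquone alone, so that the opening condition is met, and score them on the literal text.

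| Event | Item met | Score |
|---|---|---|
| A listed toxicity that meets its stated criterion (for example diarrhoea, nausea or vomiting, liver enzymes), at any time in the window | Its own item | y = 1 |
| Unlisted, but delays the end of radiotherapy by more than a week | "Any toxicity causing a delay of radiotherapy completion by greater than one week" | y = 1 |
| Unlisted, grade 3 or higher, in the run-in, no such delay | None | y = 0 |
| Unlisted, grade 3 or higher, during or after CRT, no such delay | None | y = 0 |

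Only the last two rows are affected.

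**2. Share of the window taken by the run-in.** SAP 6.1 and 6.2 give T = run-in + 45 + 84 days.

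- 7-day run-in: T = 7 + 45 + 84 = 136; 7/136 = 5.1%
- 14-day run-in: T = 14 + 45 + 84 = 143; 14/143 = 9.8%
- 21-day run-in: T = 21 + 45 + 84 = 150; 21/150 = 14.0%

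These are shares of days, not of risk.

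**3. What the model receives.** SAP 6.2 sets w = 1 if y = 1 and w = min(1, u/T) if y = 0, where u is time followed, not time on drug. If follow-up ends with the run-in, the affected patient enters as y = 0 with weight 0.05 to 0.14. Protocol 6 invites patients who stop treatment to all later visits, so the weight can reach 1. Counted as a DLT, the same patient would enter as y = 1 with weight 1.

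**4. How much one event can matter: illustration only.** The trial's model cannot be fitted without its priors. As a stand-in, take dose 1 alone, a binomial count, and assumed Beta priors (1, 1), (0.5, 0.5) and (0.48, 0.52). With x DLTs in n patients, the posterior is Beta(a + x, b + n - x). The stopping rule in Protocol 17.6 is P(p > 0.48) > 0.7.

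| Patients | Event counted | P(p > 0.48) | Event not counted | P(p > 0.48) |
|---|---|---|---|---|
| 3 | 2 DLTs | 0.72 to 0.74 | 1 DLT | 0.31 to 0.34 |
| 6 | 4 DLTs | 0.81 to 0.82 | 3 DLTs | 0.53 to 0.54 |

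For Beta(1, 1), for example, 2 of 3 gives Beta(3, 2) and P = 1 - (4 × 0.48³ - 3 × 0.48⁴) = 1 - (0.442 - 0.159) = 0.717. These counts were chosen because one event crosses the threshold. The excluded patient is given full weight as a non-event. The trial's two-parameter model would give other values.

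**The case against.** **The text can be read more broadly.** The list is introduced by a verb of inclusion, and the opening condition names atovaquone on its own. Protocol 8.6 also treats a radiotherapy interruption of more than seven days as a DLT when it is related to the trial drugs, to CRT or to both together. An investigator might well report an atovaquone-only event. DLT processing is further described in a separate Protocol Decision Point Plan that is not among these documents. This stands as evidence of intent, but the definition still says that a DLT is one of the listed items. At best the text is ambiguous.

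**The events may be rare.** Protocol 8.6 says that atovaquone alone seldom causes significant side effects, and Protocol 1.4 reports no atovaquone toxicity in the 15 treated ATOM patients. This stands as a limit on size, though no documented rate allows the expected number of affected patients to be worked out.

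**Safeguards exist.** A patient who stops in the run-in would normally fail the escalation conditions of at least three weeks of radiotherapy and at least 75% of allocated atovaquone (Protocol 17.3). A reader might infer that such a patient opens the way to the next dose. The documents do not support that; another patient would have to meet the conditions. The TMG can also depart from the model's dose. Both safeguards act on allocation and leave the score used for the final MTD unchanged.

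**A sensitivity analysis is planned.** SAP 4.2 keeps patients with more than 75% of prescribed atovaquone, plus all patients with a DLT. An early discontinuer scored y = 0 would tend to drop out as follow-up accrues. That removes the non-event but does not restore the event.

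**Conclusion.** The inconsistency is real and lies in the definition of the primary endpoint. On the literal wording, an unlisted grade 3 or higher effect due to atovaquone alone is scored as a non-DLT, both in the run-in (5% to 14% of the window) and afterwards, unless it delays the end of radiotherapy by more than a week. The direction is downward. The size is unknown: it depends on how often such events occur and how investigators read the text, and the effect on the MTD needs SAP Appendix 1.

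Three stronger readings are not supported.

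- A reader might infer that all atovaquone-only toxicity is excluded. It is not; listed items count whatever their cause within the trial treatment.
- A reader might spread the 20 patients evenly over four doses and conclude that one missed event shifts a dose's DLT rate by a fifth. The design aims to treat more patients near the MTD, and the model pools all doses, so raw proportions at a dose do not select it.
- A reader might take the sentence on skin rash in Protocol 10.2 to show that rash is expected. It only leaves the management of rash to the investigator.

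**What to change.** Reconcile the last item with the opening condition in Protocol 9.1, Protocol 14.11 and SAP Appendix 4, so that its attribution covers atovaquone alone as well as the combination. One possible wording of the attribution is: *directly related to atovaquone, alone or in combination with chemoradiotherapy*. Whether the relation must be direct or only possible, and which effects are clinically significant, is for the sponsor. Loosening the test to a possible relation for every unlisted severe effect is a debatable trade-off, because the 48% target was set from the toxicity of CRT. The sponsor should also say whether the list is exhaustive.

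As an option, the final analysis could add one re-fit that counts permanent discontinuation of atovaquone for atovaquone-related toxicity as an event. It should be limited to grade 3 or higher, because Protocol 8.6 sets no grade and a lower-grade intolerance would otherwise count.

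The cost is one sentence in a protocol amendment and in the SAP appendix, plus one model run if the option is taken. No new data are needed: the adverse event form already records severity and relationship to study drug (Protocol 14.8), so any patients already treated can be rescored. The downside is that a few more events may count as DLTs and the estimated rate may be slightly higher.
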